6.2.3. North Star Ambulatory Assessment

The NSAA consists of 17 activities, each scored as 0, 1, or 2. The sum of 16 scores (except for lifts head) will be used to form a total score [Mayhew 2013a]. Hereafter, this NSAA total score will be referred as revised NSAA (rNSAA) total score. If an activity cannot be performed due to disease progression/loss of ambulation, a score of 0 will be assigned, and will not be considered as missing. If fewer than 13 of the 16 activities are performed, the total score will be considered missing. If from 13 to 16 activities are performed, the total score will be standardized by multiplying the sum of the scores in the x activities by 16/x.

The total score will be analyzed using the similar ANCOVA after MI model as 6MWD during the overall treatment period for ITT population. The estimated difference in the change from study baseline at Week 144 will be provided. The linear transformation of the total score [Mayhew 2013a] will be analyzed using the similar ANCOVA after MI model. The total score and linear score will also be summarized by visit during overall treatment period based on ITT population.

In addition, the number of subjects with loss of function of each NSAA items (score of 1 or 2 at baseline transitioning to a 0 score post-baseline) will also be summarized by treatment groups during overall treatment period for ITT population.

The change from baseline in rNSAA total scores and linear scores will be summarized by visit for subgroups below for ITT population:

- Region (North and Latin America, Europe, Asia Pacific)
- Stop codon (UAA, UAG, UGA)
- Baseline disease severity
 - Baseline 6MWD <300 meters
 - Baseline 6MWD \geq 300 meters to <400 meters
 - Baseline 6MWD \geq 400 meters

6.2.4. Loss of Ambulation and Stair Climb/Stair Descend

Time to loss of ambulation (LoA), defined as persistent inability to perform the 10-meter run/walk test within 30 seconds at any post-baseline visit and for all remaining visits, will be evaluated using Kaplan-Meier estimation, Log-rank test, and Cox proportional hazards model (assuming similar covariates as the primary efficacy model) during overall treatment period based on ITT population. Similar analyses will be performed for time to loss of 4-stairs climb and time to loss of 4-stairs descend, defined as persistent inability to perform the 4-stairs climb test or 4-stairs descend, respectively, within 30 seconds at any post-baseline visit and for all remaining visits.

A separate analysis will evaluate time to LoA during the overall treatment period in subjects with study baseline 6MWD <300 meters.

6.2.5. Ataluren Plasma Concentration

Plasma concentration at pre-morning dose and 2 hours post-morning dose collected at the last visit (Week 144) will be summarized with descriptive statistics including n (number of subjects), arithmetic mean, standard deviation, standard error, median, minimum, and maximum, %CV, geometric mean, and geometric %CV. In addition, scatter plots and the Pearson's correlation will also be provided based on the ITT population between the ataluren plasma concentration and the following endpoints:

- change from study baseline in 6MWD
- time to 10% worsening from study baseline in 6MWD
- change from study baseline in timed function tests (10m run/walk, 4-stairs climb, 4-stairs descend)

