2.2.2. Secondary Objectives

The secondary objectives of this study are to:

- Determine the effects of ataluren on ambulation and burst activity as assessed by timed function tests (TFT)
- Determine the effects of ataluren on lower-limb muscle function as assessed by the North Star Ambulatory Assessment (NSAA)
- Assess the safety profile of ataluren
- Evaluate the correlation between plasma concentration of ataluren and functional outcomes

- Evaluate the plasma pharmacokinetic (PK) profile of ataluren

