2.3. Study Endpoints for Open-Label Treatment Period

The primary and key secondary efficacy endpoints of this study focus on the comparison of ataluren versus placebo in the double-blind treatment period (baseline to Week 72). These endpoints are described in the SAP for the double-blind treatment period.

The efficacy endpoints below focus on the comparison of subjects receiving ataluren from randomization to Week 144 (hereafter will be referred to as early-start ataluren or ataluren/ataluren) versus subjects receiving placebo from randomization to Week 72 and ataluren from Week 72 to Week 144 (hereafter will be referred to as delayed-start ataluren or placebo/ataluren) across the double-blind and open-label treatment periods.

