6.2.1.2. Time to 10% Persistent Worsening in 6MWD

Time to 10% persistent worsening in 6MWD, defined as last time that 6MWD was not 10% worse than baseline, will be evaluated using a Log-rank test and Kaplan-Meier plot, as well as a Cox proportional hazards model (assuming similar covariates as the primary efficacy model) in ITT populations. For subjects who do not have 10% 6MWD worsening, time to 10% persistent 6MWD worsening will be censored at the time of the last 6MWT during the overall period. For subjects who have all post-baseline assessments more than 10% worse than the baseline, the event will be assigned to Day 1. Subjects who become non-ambulatory will be considered to have 10% worsening at the time of becoming non-ambulatory. The proportion of 10% persistent worsening by Week 144 will also be summarized.

In addition, time to 30 meter drop in 6MWD will also be analyzed in a similar way to time to 10% persistent worsening in 6MWD.

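### The open-label SAP's exposure-function correlations treat censoring times as events for one endpoint and count placebo time for all, which weakens any relation they could show

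*SAP*

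**What the plan says.** The objective is stated in open-label SAP section 2.2.2: "Evaluate the correlation between plasma concentration of ataluren and functional outcomes". Section 6.2.5 is where the SAP gives the method. After descriptive statistics for the two Week 144 samples (pre-morning dose and 2 hours after), it states that scatter plots and the Pearson "correlation will also be provided based on the ITT population between the ataluren plasma concentration and the following endpoints". One of these is "time to 10% worsening from study baseline in 6MWD"; the others are changes from study baseline in 6MWD and in three timed function tests. The section gives no rule for censored times, no split or adjustment by arm and no restriction to time on ataluren, and does not say which of the two samples enters the correlation.

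The definitions that matter stand elsewhere:

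- **Censoring.** Section 6.2.1.2: for subjects without the event, "time to 10% persistent 6MWD worsening will be censored at the time of the last 6MWT during the overall period". Where every post-baseline assessment is more than 10% worse, "the event will be assigned to Day 1". The same section says this endpoint "will be evaluated using a Log-rank test and Kaplan-Meier plot, as well as a Cox proportional hazards model".
- **Time origin.** Section 4.3 sets study baseline at the last assessment before randomization, for both arms, and assigns it to efficacy. A separate on-ataluren baseline is assigned to safety.
- **Exposure.** Section 2.3 defines the delayed-start arm as "subjects receiving placebo from randomization to Week 72 and ataluren from Week 72 to Week 144".
- **Sampling.** Section 2.6.9 places PK sampling at Week 144; double-blind SAP section 2.7.9 says there is none in the double-blind period.

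Protocol section 9.4.8 asks for a correlation that includes time to 10% worsening and leaves its development to the SAP.

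**The concern.** Pearson's coefficient has no event indicator. A boy who never worsened is entered as though he worsened at his last walk test, and a boy who left early without worsening is entered as an early worsener.

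The second problem is timing, and it reaches every listed endpoint. A delayed-start boy who worsens at Week 36 does so on placebo, yet that time is paired with a concentration drawn 144 − 36 = 108 weeks later. Change from study baseline in 6MWD or a timed test likewise includes 72 placebo weeks in that arm. With 1:1 allocation this is about half of the ITT population.

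At stake is the reading of a stated secondary objective. A weak or absent correlation could come from the way the statistic is built rather than from the absence of an exposure-function relation.

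**Working it through.** **No plan figure to reproduce.** Section 6.2.5 gives no expected correlation, sample size or power. The figures below are an illustration of the time-to-event endpoint only.

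**Inputs from the documents:** N=359 in ITT (open-label SAP 6.2.1); 1:1 allocation (2.1); delayed-start on placebo to Week 72 (2.3); follow-up to Week 144.

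**Assumptions:** constant hazard; probability P of 10% worsening by Week 144 of 0.4, 0.6 or 0.8; standardised concentration acting on the hazard only while on ataluren, with hazard ratio (HR) 0.8 or 0.7 per SD; censoring only at Week 144; a PK sample for every subject. Section 6.2.5 omits the word persistent; I take its endpoint to be the one in section 6.2.1.2.

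**Step 1: delayed-start events before any ataluren.** Under a constant hazard, the share of events by Week 144 that fall before Week 72 is (1 − √(1 − P)) / P.

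- P=0.4: (1 − 0.775)/0.4 = 56%
- P=0.6: (1 − 0.632)/0.6 = 61%
- P=0.8: (1 − 0.447)/0.8 = 69%

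The numerators are the share of all delayed-start boys with such an event: 23%, 37% and 55%.

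**Step 2: correlation and power.** Baseline hazard h = −ln(1 − P)/144 per week, multiplied by HR^c on ataluren, where c is standardised concentration. Pearson's r is computed on observed time min(T, 144), over 3,000 runs. The comparator is a Cox score test on on-ataluren time, with delayed-start boys entering the risk set at Week 72 if event-free, over 400 runs (simulation error about 2 percentage points at 79% power). Power is at nominal two-sided 0.05.

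| HR per SD | P | r early-start | r delayed-start | r pooled | Power, pooled Pearson | Power, Cox |
|---|---|---|---|---|---|---|
| 0.8 | 0.4 | 0.125 | 0.028 | 0.076 | 30% | 59% |
| 0.8 | 0.6 | 0.157 | 0.035 | 0.096 | 45% | 79% |
| 0.8 | 0.8 | 0.186 | 0.034 | 0.111 | 56% | 84% |
| 0.7 | 0.4 | 0.202 | 0.047 | 0.125 | 67% | 94% |
| 0.7 | 0.6 | 0.245 | 0.054 | 0.150 | 82% | 99% |
| 0.7 | 0.8 | 0.285 | 0.056 | 0.171 | 91% | >99% |

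Pooling lowers r by about 40% from the early-start value throughout; for example, 1 − 0.096/0.157 = 39%.

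**Step 3: no exposure effect (HR 1.0).** Pooled Pearson rejects in 4.5% to 5.5% of runs, so false positives are not inflated.

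**Step 4: which fault costs more.** Within the early-start arm alone, at HR 0.8 and P=0.6, Pearson has 57% power and Cox 61%. With censoring only at a common end date, the censoring fault is therefore the smaller one and timing is the larger. Earlier censoring through dropout was not modelled.

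**Step 5: a stronger effect.** With 150 per arm, HR 0.6 and about 40% censored, r is 0.41 in early-start without censoring, 0.34 with censoring times used as events, 0.08 in delayed-start and 0.21 pooled. Pooled power is then about 96%.

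**The case against.** **The analysis is descriptive.** The correlation is to be provided, not tested: there is no hypothesis, alpha or decision rule, and open-label SAP section 4.7 applies no multiplicity control. No efficacy conclusion rests on it, and the same time-to-event has a proper survival analysis in section 6.2.1.2. This stands, and it limits how much weight the point carries.

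**Pooling is not spelled out.** Naming the ITT population identifies an analysis set; the SAP uses that set for between-arm comparisons too. Pooling is the literal reading, but an inference. It does not rescue the plan: shown separately, the delayed-start arm would still set placebo-period outcomes against a Week 144 concentration.

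**Only one listed endpoint is time-to-event.** Correct. For the change endpoints Pearson is a usable descriptive statistic, and preferring a rank correlation would be a matter of taste. Their fault is the time origin, and its size was not computed.

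**Stronger readings that the documents do not support.** A reader might infer that a null result would be uninterpretable; step 5 shows that a strong relation would nearly always be visible. A reader might infer that arm is confounded with exposure; at Week 144 both arms follow the same mg/kg schedule, and step 3 shows no excess of false positives. A reader might infer that concentrations exist only for boys still in the study at Week 144; protocol section 6.2.1.4 and the notes to Table 4 schedule the Week 144 procedures for premature discontinuers as well.

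**Cox does not solve everything.** A concentration taken at the last visit follows most events even in the early-start arm. This stands, and the SAP should say so.

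**Conclusion.** The concern holds as a matter of method. For time to 10% worsening, Pearson's coefficient ignores censoring that the same SAP handles correctly elsewhere. For all listed endpoints, counting from study baseline brings 72 placebo weeks into the delayed-start outcomes.

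The consequence is attenuation and loss of power. At HR 0.8 per SD and a 60% event probability, r falls from about 0.16 in early-start to 0.10 pooled, and nominal power is about 45% against 79%. At HR 0.7 and the same event probability the gap is 82% against 99%. These sizes rest on the assumed hazard, event probabilities and hazard ratios, on pooling the arms, on a sample for every subject, and on reading the endpoint as persistent worsening; none of the effect sizes comes from the documents. The double-blind comparison of ataluren with placebo is untouched.

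**What to change.** In open-label SAP section 6.2.5:

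- **Time to 10% worsening:** replace Pearson with a Cox model using log concentration as covariate, pre-dose and 2-hour samples in separate models, stratified by arm. Count time from first ataluren dose with the on-ataluren baseline, or keep the study time scale with delayed entry at Week 72. State which, because delayed entry leaves out boys who worsened on placebo. Restate the Day 1 rule for the chosen origin, and confirm that the endpoint is the persistent one.
- **6MWD and timed function tests:** show scatter plots and correlations within arm, using change from on-ataluren baseline. Pearson is acceptable as a descriptive statistic.
- **Limits to state:** concentrations come only from subjects sampled at Week 144 or at premature discontinuation, so the analysed set is smaller than ITT; a single last-visit concentration is only a proxy for earlier exposure.

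No new data are needed. The cost is SAP wording plus programming: on-ataluren baselines and windows, now assigned to safety in sections 4.3 and 4.9, must also be derived for these efficacy endpoints in the delayed-start arm.

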6.3. Exploratory Variables

6.3.1. PUL and DMD Upper Limb PROM

PUL includes 22 items (with an entry item to define starting functional level), and 21 items subdivided into shoulder level (4 items), elbow level (9 items), and distal level (8 items) dimensions. The DMD Upper Limb PROM includes 32 items categorized in 4 domains of daily life: food (7 items), self-care (8 items), household and environment (6 items), and leisure and communication (11 items). The domain sub scores will be calculated by summing the scores from all items within each domain, and the total score will be calculated as the sum of all domain scores. A domain sub score is considered missing if any of the individual item is missing within the respective domain. The total score is considered missing if any of the individual item is missing from a given assessment. The PUL and DMD Upper Limb PROM total scores will be analyzed using the similar ANCOVA after MI model as 6MWD during the overall treatment period for ITT population.

The PUL total and domain sub scores will also be summarized by age group (7 to < 8 years old, 8 to <13 years old, 13 to <22 years old, and ≥22 years old) using descriptive statistics during overall treatment period. The last assessment during the specific age group will be used for a given subject in this summary.

The number of subjects with loss of function for each PROM item by treatment group will also be summarized for ITT population during the overall treatment period.

By-visit summaries of total and domain sub scores for PUL and DMD Upper Limb PROM during overall treatment period will also be provided for subjects with the following subgroups based on ITT population:

- Baseline 6MWD <300 meters
- Baseline 6MWD \geq 300 meters to <400 meters
- Baseline 6MWD \geq 400 meters

By-visit summaries of total and domain sub scores for PUL and DMD Upper Limb PROM during overall treatment period will also be provided for subjects who lose the ability to stand from supine in <30 seconds during the study.

6.3.2. Myometry Parameters

The myometry parameters will be analyzed using the similar ANCOVA after MI model as 6MWD during overall treatment period for ITT population. The change from study baseline in myometer parameters (knee extension and elbow flexion) will be summarized at each visit during overall treatment period for ITT population.

6.3.3. Muscle Fat Fraction

The change from baseline in muscle fat fraction data (proton density fat fraction and MRS fat fraction) obtained from MRI will be summarized at each visit during overall treatment period for ITT population. The muscle fat fraction will also be summarized for subjects with the following subgroups:

- Baseline 6MWD <300 meters
- Baseline 6MWD \geq 300 meters to <400 meters
- Baseline 6MWD \geq 400 meters

6.3.4. Spirometry – Pulmonary Function Test

The change from baseline in FVC assessments (FVC, FEV1, and PEF) will be summarized in 12- or 24-week intervals from the time of LoA visit during overall treatment period for ITT population. The baseline of FVC assessment is defined as the FVC assessment taken at the visit when subjects become non-ambulatory in this analysis.

Other spirometry parameters including maximum inspiratory (MIP) and expiratory pressures (MEP) will be presented in subject listings only.

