2.2.3. Exploratory Objectives

The exploratory objectives of this study are to:

- Determine the effects of ataluren on upper-limb muscle function strength as assessed by the Performance of Upper Limb (PUL) and by the DMD Upper Limb PROM (in subjects ≥ 7 years old at baseline)
- Determine the effects of ataluren on muscle strength as assessed by myometry (in subjects < 7 years old at baseline)
- Determine the effects of ataluren on skeletal muscle integrity as assessed by magnetic resonance imaging (MRI) (at pre-qualified sites only)
- Determine the effects of ataluren on subject- and parent/caregiver-reported health-related quality of life (HRQL) as assessed by at-home questionnaire
- Determine the effects of ataluren on pulmonary function as assessed by forced vital capacity (FVC)

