2.3.3. Exploratory Endpoints

The following endpoints are considered as exploratory endpoints:

- Changes from baseline to Week 144 in PUL total score and domain subscores (in subjects ≥ 7 years old at baseline)
- Change from baseline to Week 144 in DMD Upper Limb PROM total score (in subjects ≥ 7 years old at baseline)
- Risk of loss of DMD Upper Limb PROM items over 144 weeks (in subjects ≥ 7 years old at baseline)
- Change from baseline to Week 144 in myometry parameters (in subjects < 7 years old at baseline)
- Change from baseline to Week 144 in muscle fat fraction as assessed by MRI (at pre-qualified sites only)
- Changes from baseline to Week 144 in HRQL as assessed by EQ-5D
- Change from baseline to Week 144 in FVC

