2.6.7. Spirometry

Spirometric evaluation of FVC and other parameters (eg, maximal inspiratory and expiratory pressures, peak expiratory flow) in the sitting position will be performed at screening (Visit 1), Baseline (Visit 2), and Week 72 (Visit 8), and Week 144 (Visit 11 – End of Treatment/Premature Discontinuation). If a patient loses ambulation as determined by inability to perform the 10-meter run/walk test within 30 seconds at a clinic visit, then spirometry will be performed at that visit and at all subsequent visits.

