2.3.3. Exploratory Endpoints

Exploratory endpoints include:

- Changes from baseline to Week 72 in PUL total score and domain subscores (in subjects ≥ 7 years old at baseline)
- Change from baseline to Week 72 in DMD Upper Limb PROM total score and domain subscores (in subjects ≥ 7 years old at baseline)
- Risk of loss of DMD Upper Limb PROM items over 72 weeks (in subjects ≥ 7 years old at baseline)
- Change from baseline to Week 72 in myometry parameters (in subjects < 7 years old at baseline)
- Change from baseline to Week 72 in muscle fat fraction as assessed by MRI (at pre-qualified sites only)
- Changes from baseline to Week 72 in HRQL as assessed by EuroQoL 5-Dimension (EQ-5D)
- Change from baseline to Week 72 in FVC

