6.3.4. Spirometry - Pulmonary Function Test

The change from baseline in FVC assessments (FVC, FEV1, and PEF) and %-predicted FVC will be summarized in 12-week intervals from the time of LoA visit based on both mITT and ITT populations. The baseline of FVC assessment is defined as the FVC assessment taken at the visit when subjects become non-ambulatory in this analysis.

Predicted FVC will be calculated as [Gauld 2003]:

$$\text{Predicted FVC} = \exp(0.077 * \text{ulna length} + 0.041 * \text{actual age} - 1.285)$$

%-predicted FVC will be calculated as:

$$\text{\%-predicted FVC} = \text{observed FVC} / \text{predicted FVC} * 100\%$$

Other spirometry parameters including maximum inspiratory (MIP) and expiratory pressures (MEP) will be presented in subject listings only.

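### Change in FVC from study baseline is a listed exploratory endpoint, but neither SAP specifies a summary or model of it; the only FVC analysis starts at loss of ambulation, in a subset formed after randomisation

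*SAP*

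**What the plan says.** **Endpoint.** Both SAPs have an exploratory objective on pulmonary function, with a matching endpoint in section 2.3.3. The double-blind SAP lists "Change from baseline to Week 72 in FVC" and the open-label SAP lists "Change from baseline to Week 144 in FVC". Protocol sections 2.2.1.3 and 2.2.2.2 list the same two.

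**Collection.** Open-label SAP section 2.6.7 says that spirometry "in the sitting position will be performed at screening (Visit 1), Baseline (Visit 2), and Week 72 (Visit 8), and Week 144". Protocol section 6.2.13 and double-blind SAP section 2.7.7 agree for the visits they cover. Spirometry becomes more frequent only for a boy who loses ambulation, from that visit onward.

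**Analysis.** Section 6.3.4 of the double-blind SAP says that the FVC measures "will be summarized in 12-week intervals from the time of LoA visit based on both mITT and ITT populations". Section 6.3.4 of the open-label SAP says that they "will be summarized in 12- or 24-week intervals from the time of LoA visit during overall treatment period for ITT population". Both then state: "The baseline of FVC assessment is defined as the FVC assessment taken at the visit when subjects become non-ambulatory in this analysis". Section 3.3.4 of the document on changes from the planned analysis leaves this as it is. FVC does not appear among the changes from the protocol in section 8 of either SAP.

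**The concern.** The endpoint asks whether FVC changes differently from study baseline in the two randomised arms. The analysis asks how FVC changes after a boy has stopped walking. These are different questions, and only the second has a planned table.

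The second cannot stand in for the first. A boy enters the summary only by losing ambulation, which happens after randomisation and which treatment is meant to delay. If it does delay it, the boys who reach that point may differ between arms in number, age and severity. Any effect on FVC before loss of ambulation is also subtracted out by the new baseline. The stated lung-function objective would then be left without a randomised comparison, although the data for one are collected.

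**Working it through.** The plan gives no figure to reproduce on this point, so the check is mainly a side-by-side reading.

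| | Listed endpoint (section 2.3.3, both SAPs) | Specified analysis (section 6.3.4, both SAPs) |
|---|---|---|
| Baseline | Study baseline | FVC at the loss-of-ambulation visit |
| Time axis | To Week 72 or Week 144 | 12-week (double-blind) or 12- or 24-week (open-label) intervals after that visit |
| Boys who can contribute | All with FVC at both visits | Only those with loss of ambulation and a later FVC |
| Comparison protected by randomisation | Yes, before missing data | No |

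**Step 1: does naming the ITT population bring everyone in?** No. Inclusion criterion 10 requires every boy to complete the timed tests within 30 seconds at entry, and double-blind SAP section 6.2.2.4 repeats this. Nobody therefore has lost ambulation at baseline. A boy who stays ambulant has no loss-of-ambulation visit and so no baseline in this analysis. A boy whose loss is first seen at his last visit has a baseline but no change value.

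**Step 2: is the selecting event an outcome?** Yes. Time to loss of ambulation is a secondary endpoint in both SAPs (section 2.3.2).

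**Step 3: does another sentence supply the missing analysis?** In the open-label SAP, section 4.3 and the opening of section 6 set study baseline for efficacy, with by-visit summaries by treatment group. Section 6.3.4 replaces both the baseline and the time axis for FVC. Double-blind SAP section 4.2 allows an exception to its baseline rule, and section 6.3.4 uses it. By contrast, open-label SAP sections 6.3.2 (myometry) and 6.3.3 (muscle fat fraction) summarise change from baseline at each visit in ITT.

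**Step 4: a consequence of the design in the open-label report.** Take two boys who both lose ambulation at Week 48. The early-start boy has had 48 weeks of ataluren and the delayed-start boy none. The delayed-start boy's first 24 weeks after loss (Week 48 to Week 72) are on placebo. The interval since loss of ambulation therefore does not mean the same exposure in the two arms.

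**Step 5: how many boys?** The study population is 359 (open-label SAP section 6.2.1). The share losing ambulation is an assumption, since no document gives it. Boys who can have the new baseline = 359 × share:

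- 5%: 359 × 0.05 = 18
- 10%: 36
- 20%: 72
- 30%: 108
- 40%: 144
- 50%: 180

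These are upper limits, because a later FVC is also needed. Change from study baseline could use up to 359, before missing data.

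**The case against.** **The endpoint is exploratory and the summary is descriptive.** FVC is outside the fixed testing sequence, section 6.3.4 promises no test or model, and no claim of a treatment effect is attached to it. This stands, and it limits the weight of the point. It does not fill the gap, because the listed endpoint still has no table.

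**The loss-of-ambulation view has a reason.** Spirometry is intensified from that visit, and the protocol's disease background describes respiratory weakness as a later development. This stands as a reason to keep the summary, not as a reason to have no other.

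**FVC is not wholly unreported.** A reader might infer that FVC is never looked at. The documents do not support that: both SAPs plan by-subject listings for every eCRF domain. The exact statement is that no summary or model of change from study baseline is specified.

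**The protocol may have planned it this way.** The protocol text available runs from 9.4.3 to 9.4.5 and from 9.4.5.3 to 9.4.7, so its own analysis text for FVC cannot be seen. Nothing is claimed here about what the protocol planned beyond its endpoint lists.

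**Conclusion.** The point holds as a mismatch between endpoint and analysis in both SAPs. It follows from the text alone: section 6.3.4 sets its own rule, and that rule excludes every boy who stays ambulant. The selection problem is present whatever the share losing ambulation. The 18 to 180 boys in the working rest on the assumed 5% to 50%.

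Three further readings are tempting but not supported:

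- **That the subset is small.** No rate of loss of ambulation is given, and protocol section 11.2.4 describes a high near-term risk in boys below 300 metres, who could enrol from 150 metres. Over 144 weeks the share could be large.
- **That precision falls by a stated factor.** A ratio of standard errors based on the numbers of boys would need equal SDs for two different quantities: change over 72 or 144 weeks from study baseline, and change over shorter intervals after loss of ambulation. The documents give neither SD.
- **That the summary favours one arm.** The comparison is unprotected, but the documents do not allow the direction of any bias to be determined.

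No primary or key secondary conclusion changes. The plan should still be corrected, because a listed endpoint would otherwise go without a result.

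**What to change.** Add the following to section 6.3.4, by arm in the ITT population:

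- **Week 72:** FVC and its change from study baseline, ataluren versus placebo. Label this post hoc. The first database lock was on 11 April 2022, and the changes document already reports treatment differences.
- **Week 144:** the same for early-start versus delayed-start ataluren, which is the contrast defined in open-label SAP section 2.3. Record the date of the addition relative to the final lock.
- **Form:** a by-visit summary and, preferably, an ANCOVA with baseline FVC, baseline age, baseline height, treatment and the three stratification factors. A repeated-measures model would add little at Week 72, because boys who stay ambulant have only one scheduled post-baseline spirometry in the double-blind period.
- **Scale:** use absolute FVC. The %-predicted formula in the double-blind SAP needs ulna length, which protocol section 6.2.6 asks for only when a boy cannot stand. Height is measured at every clinic visit.

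Keep the loss-of-ambulation summary, and state that it is descriptive and not a randomised comparison. Note the FVC change in section 8 of the amended plan. The cost is one more table per report, with no new data collection.
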